Study Day1: Using the data from the dose ranging study a full pharmacokinetic study will be undertaken. Participants will arrive at the St. John McMichael Centre (Hammersmith

hospital) having fasted from the previous evening and a canulae will be inserted into a peripheral vein. Blood samples (10ml) will be taken at -10 and 0 post oral propionate administration (3g) then 4 samples will be taken during each of the absorption and early elimination phases, followed by further samples post peak for a total of 6 samples in this phase, over three half-lives. In total 120mls of blood will be drawn.

Study Day 2: At least a week following the first study day participants will be asked to attend a repeat visit at the St John Mc Michael Centre which will follow the same protocol as for study day 1 but participants will be given a 6g dose of propionate.

Blood samples will be analysed using the following methods:

- Propionate by Mass spectrometry
- Insulin, GLP-1, PYY, leptin and non-esterified fatty acids will be measured using commercially available kits.
- Glucose will be measured using a glucometer.

Study 2

Aim: To dose dependently determine if propionate augments beta cell function.

Study methodology: Participants will undergo a series of oral glucose tolerance tests (OGTT) following administration of propionate. Each participant will receive all doses of propionate and each study day will be separated by at least 1 week.

Participants: 30 healthy men and women aged 18-70, body mass index (BMI) 20-25 kg/m², with normal fasting glucose and HbA1C.

Support for number of participants: A previous small study of the effects of propionate on glucose levels in humans identified a 47.4% reduction in glucose AUC over 2 hours following consumption of a standard 50 g carbohydrate load supplemented with propionate. Mean OGTT glucose AUC in a group of 514 healthy subjects was 40.8 mmol.min (SD 7.1 – unpublished data from the study described in Diabetic Medicine 2007;24:1269-1278). A 47.4% reduction in OGTT glucose AUC would result in a mean glucose AUC of 21.5. Using data from the same study, a mean insulinogenic index of 0.99 (SD 0.85) was observed, regression analysis estimated that a 47.4% reduction in glucose AUC would be associated with an increase in insulinogenic index of 0.73 SD. This can be detected as significant at p<0.05, with 80% power using 30 in each group. Screen failures will be replaced.

Health Screening and enrolment Visit

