Participants will arrive fasted from 8pm the previous evening. They will be clerked and examined by a research doctor. Measurements of height, weight, body fat content, blood pressure , an ECG and a blood test (for full blood count, urea and electrolytes, liver function tests, lipid profile, fasting glucose, HbA1C) will be taken. Screen failures will be replaced.

Study Day 1-5 Participants will undergo a frequently sampled oral glucose tolerance test (OGTT) to detect changes in insulin sensitivity and beta cell function. Participants will be asked to refrain from strenuous exercise and alcohol on the day prior to each study. They will be asked to eat a standard meal of your choice before the study (e.g. ready-made meal) and then be required to fast overnight.

They will be asked to come to the Clinical Investigations Unit at Hammersmith Hospital at 8:30am, having fasted from 8pm the previous day. A small plastic tube (cannula) will be inserted into their arm and a blood sample taken. This will be in place for the duration of the study day. Baseline blood samples will be taken at -30 and -10mins before the participant will take capsules containing either sodium chloride (placebo control) or sodium propionate. They will then consume a 250 ml drink containing 75 g of glucose at a pre-determined time so that the expected peak blood glucose level coincides with the expected peak propionate blood concentration. During the next 3 hours they will have blood samples taken at 0, 10, 20, 30, 60, 90, 120, 180 mins after the glucose drink. A total of 90 ml of blood will be taken (about 6-8 tablespoons of blood). These will be taken through the cannula. After 3 hours the cannula will be removed and the participant will be provided with a light snack and able to go home.

Participants will be asked to attend four repeat visits with a minimum of a week between visits. They will randomly be assigned an oral dose of propionate, either 0, 1, 3, 6, 9g.

Blood samples will be analysed using the following methods:

- Propionate by Mass spectrometry
- Insulin, GLP-1, PYY, leptin and non-esterified fatty acids will be measured using commercially available kits.
- Glucose will be measured using a glucometer.

Study 3

Aim: To determine the effect of propionate on beta cell function using the gold standard intravenous glucose tolerance (IVGTT) test in healthy participants and healthy volunteers at risk of developing diabetes.

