Study methodology: Participants will undergo intravenous glucose tolerance tests. The effect of propionate on beta cell function will be determined in a randomised double blind placebo controlled crossover study.

Participants:

Cohort 1: 34 healthy men and women aged 30-70, body mass index (BMI) 25-35 kg/m², normal fasting blood glucose (below 5.5mmol/l and HbA1C less than 5.7% will be eligible to volunteer. Screen failures will be replaced.

Cohort 2: 34 men and women at risk of developing diabetes aged 30-70 with a body mass index (BMI) 25-35 kg/m² with fasting blood glucose between 5.6mmol/l and HbA1C between 5.8 and 6.5% will be eligible to volunteer. Screen failures will be replaced.

Support for number of participants: Our pilot data demonstrates mean Insulin AUC₁₀ of 8.1 for saline treated mice versus 11.3 for mice propionate-treated mice, an increase in the acute insulin response to glucose of 40%. Mean IVGTT-AIRg in a group of 306 healthy subjects was 492 mU.min (SD 48.7 - unpublished data from the study described in Diabetologia 2004;47:1157-1166). Using log-transformed data for IVGTT-AIRg, it was estimated that a 40% increase in IVGTT-AIRg would constitute an increase of 0.79 SD, which could be detected as significant at p<0.05, with 90% power using 34 in each group. Screen failures will be replaced.

Health Screening and enrolment Visit

Participants will arrive fasted from 8pm the previous evening. They will be clerked and examined by a research doctor. Measurements of height, weight, body fat content, blood pressure, an ECG and a blood test (for full blood count, urea and electrolytes, liver function tests, lipid profile, fasting glucose, HbA1C) will be taken. Screen failures will be replaced.

Visit 1: Oral glucose tolerance test.

The participant will be asked to come to the Clinical Investigations Unit at Hammersmith Hospital at 8:30am, having fasted from 8pm the previous day. A cannula will be inserted into a peripheral vein and two fasting blood samples taken at -30 and -10 mins before the participant consumes a drink containing 75 g of glucose. During the next 3 hours blood samples will be taken at 0, 10, 20, 30, 60, 90, 120, 180 minutes post glucose administration. A total of 100ml of blood will be taken.

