7. STATISTICS AND DATA ANALYSIS

An independent researcher (i.e. not linked to the study) will be given the task of randomisation, which will be by sealed envelopes.

Although the data handling and statistical methodology can only be confirmed once all the data is collected. Our intention is to use parametric techniques to analyse the data if it is normally distributed. We will therefore use T-tests for comparisons between two groups and ANOVA for comparisons of three or more groups.

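### Studies 2 and 3 compare conditions within people, but Section 7 names only t-tests and ANOVA for groups, defers the method until the data are in, and names no test of dose-dependence

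*Combined protocol and SAP*

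**What the plan says.** Section 3 makes both studies within-person. For Study 2: "Each participant will receive all doses of propionate and each study day will be separated by at least 1 week". The levels appear under the study days: "They will randomly be assigned an oral dose of propionate, either 0, 1, 3, 6, 9g". For Study 3: "The effect of propionate on beta cell function will be determined in a randomised double blind placebo controlled crossover study", with a second visit at least a week later, in each of two cohorts of 34.

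The Study 2 aim is a dose-response question: "To dose dependently determine if propionate augments beta cell function". The Study Summary calls Study 2 open label. It also states an overall aim of finding how diabetes risk affects the response, which requires comparing Cohort 1 with Cohort 2 in Study 3.

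Section 7 is short. On timing: "Although the data handling and statistical methodology can only be confirmed once all the data is collected". It intends parametric methods if the data are normal, and then: "We will therefore use T-tests for comparisons between two groups and ANOVA for comparisons of three or more groups". The available text has no participant or period term, no paired or repeated-measures form, no dose contrast and no multiplicity rule.

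For Study 2 the sample-size paragraph takes an effect of 0.73 SD and concludes: "This can be detected as significant at p<0.05, with 80% power using 30 in each group". The Study 3 paragraph takes 0.79 SD on log-transformed AIRg and arrives at 34 per group for 90% power.

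**The concern.** Observations on the same person at different visits are usually positively correlated. A between-groups test ignores this: it puts the stable differences between people into the error term, although they cancel from every treatment comparison. Standard errors are then too large, the real type I error is below 5%, and the efficiency that justifies a crossover is lost.

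Three further gaps follow from the same paragraph.

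- An omnibus ANOVA over five doses asks whether any dose differs. It does not directly test dose-dependence.
- The comparison of the two cohorts is properly between people, but it should be made on each person's propionate-minus-placebo difference. Section 7 does not say so.
- Study 2 is open label, so leaving the method until the data are in allows the form of test to be chosen with results in view. This does not depend on any assumed correlation.

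**Working it through.** **Inputs from Section 3.** Study 2: n = 30, five doses (0, 1, 3, 6, 9 g), 0.73 SD, 80% power. Study 3: n = 34 per cohort, 0.79 SD on the log scale, 90% power. Alpha 0.05, sidedness not stated.

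**Assumptions, not in the documents.** Within-person correlation rho; dose shape; normal data with equal variances and equal correlations between visits, unless stated otherwise.

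**1. The plan's own figures.** Independent groups, two-sided, n per group = 2(z₁ + z₂)²/d²:

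- Study 2: 2 × (1.960 + 0.842)² / 0.73² = 29.5, rounded up to 30.
- Study 3: 2 × (1.960 + 1.282)² / 0.79² = 33.7, rounded up to 34.

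The one-sided version gives 24 and 28, so the sizing was two-sided. Had the effects been in SDs of the within-person difference, the factor 2 would drop out, giving 14.7 and 16.8. The sizing therefore takes no credit for pairing; it equals assuming rho = 0.

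**2. Sized two-condition comparisons.** The true variance of the mean difference is 2(1 − rho)/n, but an unpaired test estimates 2/n. Paired power uses the noncentral t with d/√(2(1 − rho)); unpaired figures for rho above 0 are simulated.

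| rho | 0 | 0.3 | 0.5 | 0.7 |
|---|---|---|---|---|
| Type I error, unpaired | 5% | 2.0% | 0.7% | 0.1% |
| Study 2 power, unpaired | 79% | 84% | 87% | 92% |
| Study 2 power, paired | 78% | 90% | 97% | 99.9% |
| Study 3 power, unpaired | 89% | 93% | 96% | 98% |
| Study 3 power, paired | 88% | 96% | 99% | >99.9% |

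The cohort comparison, if built from four cells treated as independent, has type I error of 2.0 / 0.6 / 0.1% at rho 0.3 / 0.5 / 0.7.

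**3. Five-dose ANOVA run between groups, type I error.** At rho 0 / 0.1 / 0.3 / 0.5 / 0.7: about 5 / 3.3 / 1.0 / 0.1 / <0.1% (simulation, 145 error df).

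**4. Power of the overall dose test, linear shape.** The mean dose is 19/5 = 3.8 g, and squared deviations sum to 14.44 + 7.84 + 0.64 + 4.84 + 27.04 = 54.8. With a rise of 0.73/9 SD per gram, noncentrality is 30 × 54.8 × (0.73/9)² = 10.8 at rho 0. Within-person it is 10.8/(1 − rho) = 15.5 / 21.6 / 36.1 at rho 0.3 / 0.5 / 0.7. The noncentral F (4 and 116 df) gives 88.7 / 97.0 / 99.9%. Run between groups on correlated data, simulation gives 72 / 71 / 70%. At rho 0 both are about 73 to 74%.

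**5. Other shapes, largest effect 0.73 SD, rho 0.3 / 0.5 / 0.7.**

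| Shape | Between groups | Within-person |
|---|---|---|
| Plateau from 3 g | 87 / 88 / 89% | 96 / 99 / >99.9% |
| Plateau from 1 g | 82 / 82 / 83% | 94 / 99 / >99.9% |
| Peak at 3 g | 62 / 60 / 55% | 82 / 94 / 99.7% |

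Whether the between-groups test falls below 80% therefore depends on the shape.

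**6. Validity of a trend test.** If people's own dose slopes vary (assumed SD 0.3 / 0.5 / 0.73 at 9 g, rho 0.5, no mean effect), a linear contrast on the pooled residual rejects about 6 / 8 / 10%, not 5%. A one-sample t-test on each participant's slope stays at about 5%. With equal slopes its power for the linear shape (29 df, noncentrality √15.5, √21.6, √36.1) is about 97 / 99 / >99.9%, almost the same as the pooled contrast (97 / 99.6 / >99.9%).

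**The case against.** The best defence is that a paired t-test is a t-test and repeated-measures ANOVA is an ANOVA. The protocol also uses the word groups loosely: the Study Summary speaks of intervention and control groups although Studies 2 and 3 are within-person. Sizing by an independent-groups formula shows how n was set, not how the data will be analysed. All of this stands. Section 7 is open rather than wrong. It does not, however, answer the deferral of the method or the missing test of dose-dependence.

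A reader might infer more than the documents support:

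- **False positives or an undersized trial.** With positive correlation an unpaired test is conservative, and the sized comparisons essentially keep their power.
- **A weaker test leading to a worse dose in Study 3.** With complete data the five dose means are the same under either analysis; only the error term changes. A choice made on the means would be unaffected, and no passage says the choice rests on significance. The plan gives no selection rule, which is a separate gap.
- **Skewness pulling power well below 80%.** The Study 2 paragraph reports that "a mean insulinogenic index of 0.99 (SD 0.85) was observed", which suggests skew. But the result depends on how the effect acts. Under a matched lognormal on the raw scale, the plateau from 3 g has between-groups power of 50 / 46 / 42% at rho 0.3 / 0.5 / 0.7 if the effect is multiplicative, and about 85% if it is additive. The documents do not say which applies.

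**Conclusion.** The point holds as a gap in specification that should be fixed; it is not a fatal flaw. The within-person designs, the group-based wording, the deferred method and the absence of a dose-dependence test can all be read directly from the text.

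The size is conditional. If the tests are run between groups and rho is 0.3 to 0.7, the five-dose ANOVA works at 1% or less instead of 5%. For a linear response it gives up roughly 17 to 30 percentage points of power (72 against 89%; 70 against 99.9%). At rho 0.1 the error rate is still 3.3%, and at rho 0 nothing is lost. Rho and the dose shape are assumptions throughout. The harm is lost efficiency, wrong error bars, and a form of test that could be settled after open-label results are known.

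**What to change.** Before any Study 2 data are seen, replace the Section 7 sentence that defers the methodology and, for Studies 2 and 3, the sentence on t-tests and ANOVA, with:

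> Treatment and dose comparisons in Studies 2 and 3 will use a linear mixed model with treatment (dose) and period as fixed effects and participant as a random effect. Study 3 AIRg will be log-transformed, as in the sample-size calculation. Cohorts 1 and 2 will be compared by the treatment-by-cohort interaction, that is, on within-person differences. In Study 2 the within-person overall test of dose is primary at 5%. Dose-dependence is tested by a prespecified secondary linear contrast, computed from each participant's own slope (one-sample t-test) or with a random slope. Comparisons of each dose with 0 g are secondary and adjusted by [named method, for example Holm or Dunnett-type].

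Also state one scale, raw or log, for the insulinogenic index.

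Which of the overall test and the trend test is primary is the sponsor's choice, provided one is fixed in advance; letting either decide gives 8.4 to 8.7% type I error. The overall test gives up some power if the response is truly linear (89 / 97 / 99.9% against about 97 / 99 / >99.9% for the slope test). In return it guards against non-linear shapes: for the peak at 3 g a pooled linear contrast has only 16 / 20 / 30%.

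**Cost.** Slightly more analysis work; no new participants, visits or samples. Period adjustment costs almost nothing if dose orders are balanced. Adjusted comparisons with 0 g are weaker: with Bonferroni over four, 0.73 SD and n = 30, paired power is about 57 / 76 / 90 / 99% at rho 0 / 0.3 / 0.5 / 0.7. The stated 80% should not be claimed for them at low rho.

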8. REGULATORY ISSUES

ETHICS APPROVAL

This study is awaiting ethical approval from the West London Research Ethics Committee. The study will be conducted in accordance with the recommendations for physicians involved in research on human subjects adopted by the 18th World Medical Assembly, Helsinki 1964 and later revisions.

CONSENT

Consent to enter the study must be sought from each participant only after a full explanation has been given, an information leaflet offered and time allowed for consideration. Signed participant consent should be obtained. The right of the participant to refuse to participate without giving reasons must be respected. After the participant has entered the study the clinician remains free to give alternative treatment to that specified in the protocol at any stage if he/she feels it is in the participant's best interest, but the reasons for doing so should be recorded. In these cases, the participants remain within the study for the purposes of follow-up and data analysis. All participants are free to withdraw at any time from the protocol treatment without giving reasons and without prejudicing further treatment.

CONFIDENTIALITY

The Chief Investigator will preserve the confidentiality of participants taking part in the study and is registered under the Data Protection Act. Results will be stored on our departmental database. This is a confidential computer system which requires a specific password for access. Only authorised members of the Imperial College Healthcare Trust and Department of Investigative Medicine will have this password. The system can only be accessed from within the hospital. Researchers themselves will undertake analysis of data stored on the shared drive. This will take place at the Imperial College Healthcare Trust. Any other data collected from participants will be kept in locked storage in the Department of Investigative Medicine, under the authority of [name].

INDEMNITY

Imperial College holds negligent harm and non- negligent harm insurance policies which apply to this study.

SPONSOR

Imperial College London will act as the main sponsor for this study. Delegated responsibilities will be assigned to the NHS trusts taking part in this study.

FUNDING

National Health Institute for Research will be funding this study.

Participants will be reimbursed for their time at the rate of £33 per visit.

AUDITS AND INSPECTIONS

The study may be subject to inspection and audit by Imperial College London under their remit as sponsor and other regulatory bodies to ensure adherence to GCP and the NHS Research Governance Framework for Health and Social Care (2nd edition).

10. PUBLICATION POLICY

The findings of the research will be published in an open-access, peer-reviewed journal. In addition we will be collaborating with patient groups and professional groups to disseminate the findings via multiple media channels such as patient association publications, print and broadcast media.
